#### Treatment Emergent Adverse Events (TEAE)

Adverse events (AEs) starting on or after the first dose of IP as determined by the flag indicating if the adverse event started prior to the first dose of IP on the Adverse Events Summary CRF and up to 30 days after the last dose date or EOS date, whichever is **earlier**.

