Abbreviation or Term	Definition/Explanation
%CV	coefficient of variation
ADA	Anti-drug antibody assay
ADME	Absorption, distribution, metabolism, and excretion
ALP	alkaline phosphatase
ALT	alanine aminotransferase
API	Active pharmaceutical ingredient
AST	aspartate aminotransferase
AUC	area under the concentration-time curve
AUC _{last}	area under the concentration-time curve from time 0 to the time of the last quantifiable sample
BMI	Body Mass Index
CaSR	Calcium sensing receptor
Ca	Calcium
cCa	Total serum albumin corrected calcium concentration
cCa x P	Corrected calcium-phosphorus product
CHD	Coronary heart disease
CKD	Chronic kidney disease
CKD-MBD	Chronic kidney disease-mineral and bone disorder
CI	Confidence Interval
CK	Creatinine kinase
CL	Clearance
C _{max}	Maximum observed concentration
Corrected Total Serum Calcium (for albumin levels < 4.0 g/dL)	Corrected calcium (mg/dL) = Total calcium (mg/dL) + (4 - albumin [g/dL])*0.8.
CRF	Case report form (electronic or paper)
CTCAE	Common Terminology Criteria for Adverse Events
CV	Coefficient of variation
DILI	Drug-induced liver injury
EDC	Electronic data capture
ECG	Electrocardiogram
End of study for individual subject	defined as the last day that protocol-specified procedures are conducted for an individual subject
End of treatment	defined as the last assessment for the protocol-specified treatment phase of the study for an individual subject

Abbreviation or Term	Definition/Explanation
Enrollment Date	Same as Study Day 1
EOS	End of Study
eSAE	electronic Serious Adverse Event (form)
FDA	Food and Drug Administration
FIH	first-in-human
FSH	follicle-stimulating hormone
GCP	Good Clinical Practice
GGT	gamma-glutamyl transpeptidase
GM	Geometric mean
HBcAb	hepatitis B core antibody
HBsAg	hepatitis B surface antigen
HDL-C	high density lipoprotein cholesterol
hERG	human Ether-à-go-go-Related Gene
HepCAb	hepatitis C virus antibodies
HIV	human immunodeficiency virus
HR	heart rate
ICF	informed consent form
ICH	International Conference on Harmonisation
IFU	instructions for Use
INR	international normalized ratio
Interdialytic AUC _{last}	area under the concentration-time curve measured from the time of drug administration to the beginning of the next dialysis session
Interdialytic C _{max}	maximum drug concentration measured between the time of drug administration to the beginning of the next dialysis session
IP	investigational product
IPIM	investigational product instruction manual
iPTH	Intact parathyroid hormone

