IP will be administered at the end of dialysis on Study Days 1, 3, 6, 8, 10, 13, 15, 17, 20, 22, 24, 27 (12 doses). Investigational product will be administered by bolus injection into the venous line of the dialysis circuit at the end of hemodialysis treatment, prior to or during rinse-back with each hemodialysis session (ie, 3 times per week). At least 150 mL of rinse back volume should be administered after investigational product injection to ensure investigational product reaches the systemic circulation. If rinse-back is completed and investigational product was not administered, then investigational product may be administered intravenously followed by at least 10 mL saline flush volume. The end of hemodialysis treatment is defined as when the prescribed hemodialysis treatment time is completed (ie, remaining time on dialysis (RTD) is zero) or when the arterial flow is stopped (eg, arterial line is clamped or disconnected to discontinue treatment), whichever occurs first. If a regularly scheduled hemodialysis session is missed and subsequently rescheduled, investigational product will not be administered at the rescheduled hemodialysis session. For example, a subject on a Mon/Wed/Fri schedule who misses a Wed session will be dosed on Mon and Fri; if a make-up session is added on Thu and the subject maintains the regularly scheduled session on Fri, the subject will only be dosed on Mon and Fri and not on Thu. If an additional hemodialysis treatment is needed intermittently (eg, fourth treatment during a week for ultrafiltration) then an additional dose of investigational product will not be administered during the extra dialysis session. Additional details will be provided in IPIM. Investigational product must only be administered intravenously; it must not be administered via any other route. Investigational product must not be administered concurrently with any other intravenous medications. If there is a significant permanent change to the hemodialysis prescription, then the sponsor will be notified and subject may be withdrawn from treatment with investigational product.

Blood samples for the determination of PK parameters will be collected on Day 1 and 27 at predialysis, and at 10, 30, 60 and 90 min postdose and on Day 2 and 28 between

18 and 30 h after study drug administration, and at predialysis on Days 3, 8, 15, 22, 29, 34, 41, and 55 and at 10 min postdose on Days 8, 15 and 22.

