The date and time of hemodialysis treatment will be recorded throughout the treatment period. When a visit corresponds to a dialysis day, study procedures should be completed prior to hemodialysis.

Following completion of all study procedures on Day 1, subjects will be discharged with instructions to return to the research facility at specified time points for dosing, collection of blood samples for PK, PD and completion of safety assessments (including blood samples for antibody analysis) through the end of the study according to the schedule of assessments.

- Other Predialysis Assessments after Day 1:
 - Body Weight (before dialysis) on Days 29 and 55
 - Physical exam on Days 15, 29 and 55
 - Vital signs (BP,HR,RR, TEMP) – all visits
 - 12 lead Electrocardiograms (ECG) on Day 28 and Day 55 (EOS)
 - Adverse event monitoring (including serious adverse events and deaths) – all visits
 - Concomitant medications – all visits
 - Pregnancy test on Day 34
 - Hematology, PT, aPTT on Days 15, 29 and 55
 - Clinical Chemistry on Days 15, 29 and 55
 - Albumin on Days 3, 8,15, 22, 27, 29, 34, 41, 55
 - Phosphorus on Days 3, 8, 15, 22, 27, 34, 41, 55
 - Calcium (cCa) on Days 8, 15, 22, 27, 29, 34, 41, 55
 - iPTH on Days 8, 15, 22, 27, 34, 41, and 55
 - Anti-Drug Antibodies on Day 29 and 55

Subjects will be followed for safety throughout the 4-week treatment period and for 4 weeks after the last dose of investigational product to Day 55 (EOS). Dosing with investigational product may be suspended, for low predialysis iPTH or cCa, symptomatic hypocalcemia, or other drug-related adverse events.

Subjects who test positive for antibodies to AMG 416 at the EOS visit will be asked to return for additional follow-up testing (see [section 7.4](#))

If there is a clinically significant clinical or laboratory abnormality that requires monitoring, subjects will be followed until resolution of the abnormality or until it is considered stable.

Subject participation is complete once Day 55 end-of-study (EOS) procedures are performed.

For a full list of study procedures, including the timing of each procedure, please refer to the [Schedule of Assessments](#).

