8. WITHDRAWAL FROM TREATMENT, PROCEDURES, AND STUDY

8.1 Subjects' Decision to Withdraw

Subjects have the right to withdraw from the study at any time and for any reason without prejudice to their future medical care by the physician or at the institution.

Subjects (or a legally acceptable representative) can decline to continue receiving investigational product and/or other protocol required therapies or procedures at any time during the study but continue participation in the study. If this occurs, the investigator is to discuss with the subject the appropriate processes for discontinuation from investigational product or other protocol required therapies and must discuss with the subject the options for continuation of the Schedule of Assessments ([Table 1](#)) and collection of data, including endpoints and adverse events. The Investigator must document the change to the Schedule of Assessments ([Table 1](#)) and the level of follow-up that is agreed to by the subject (eg, in person, by telephone/mail, through family/friends, in correspondence/communication with other physicians, from review of the medical records).

Withdrawal of consent for a study means that the subject does not wish to receive further protocol-required therapies or procedures, and the subject does not wish to or is unable to continue further study participation. Subject data up to withdrawal of consent will be included in the analysis of the study, and where permitted, publically available data can be included after withdrawal of consent. The investigator is to discuss with the subject appropriate procedures for withdrawal from the study.

8.2 Investigator or Sponsor Decision to Withdraw or Terminate Subjects' Participation Prior to Study Completion

The investigator and/or sponsor can decide to withdraw a subject(s) from investigational product and/or other protocol required therapies, protocol procedures, or the study as a whole at any time prior to study completion.

Subjects may be eligible for continued treatment with Amgen investigational product(s) and/or other protocol required therapies by a separate protocol or as provided for by the local country's regulatory mechanism, based on parameters consistent with [Section 12.1](#).

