9.2.2 Reporting Procedures for Serious Adverse Events

The investigator is responsible for ensuring that all serious adverse events observed by the investigator or reported by the subject that occur after signing of the informed consent through 30 days after the last dose of investigational product or Day 55 End of Study, whichever is later are recorded in the subject's medical record and are submitted to Amgen. All serious adverse events must be submitted to Amgen within 24 hours following the investigator's knowledge of the event via the applicable CRF.

After the protocol-required reporting period defined above, the investigator does not need to actively monitor subjects for serious adverse events. However, if the investigator becomes aware of a serious adverse event after this protocol-required reporting period, the investigator will report the event to Amgen within 24 hours of the investigator's knowledge of the event. Serious adverse events reported outside of the protocol-required reporting period will be captured within the safety database as clinical trial cases for the purposes of expedited reporting.

If the electronic data capture (EDC) system is unavailable to the site staff to report the serious adverse event, the information is to be reported to Amgen via an electronic Serious Adverse Event (eSAE) Contingency Report Form within 24 hours of the investigator's knowledge of the event. See [Appendix B](#) for a sample of the eSAE Contingency Report Form. For EDC studies where the first notification of a serious adverse event is reported to Amgen via the eSAE Contingency Report Form, the data must be entered into the EDC system when the system is again available.

The investigator must assess whether the serious adverse event is possibly related to the investigational product. This relationship is indicated by a "yes" or "no" response to

the question: “Is there a reasonable possibility that the event may have been caused by the investigational product?”

The investigator must assess whether the serious adverse event is possibly related to any study mandated activity or procedure. This relationship is indicated by a “yes” or “no” response to the question: “Is there a reasonable possibility that the event may have been caused by a study activity/procedure?”

The investigator is expected to follow reported serious adverse events until stabilization or reversibility.

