**Enrollment Date** 

The date a subject is randomized to a treatment group by the interactive voice/web response system (IXRS) after they have satisfied all enrollment criteria.

Randomization Date

The randomization date is the same as the enrollment date.

Study Week

The 7-day periods beginning with Study Day 1.

Study Day 1

The first day that investigational product is administered to the subject. For subjects who did not receive any investigational product during the study, Study Day 1 will be the randomization day.

Study Day

For each subject and for a given study visit date, study day is defined as the number of days since Study Day1:

Study day = (study visit date - Study Day 1 date) + 1

If the date of interest is prior to study day 1, study day will be calculated as

Study day = (study visit date – Study Day 1 date).

**Product:** Etelcalcetide (AMG 416) Protocol Number: 20140197 Page 8 of 20

Date: 26 November 2018

Date of Last Dose IP Received

For each subject, the last investigational product dose date is defined as the date when

the last non-missing dose of investigational product is administered (zero dose is still

counted).

Primary Completion

The time when the last subject is assessed or receives an intervention for the purposes

of final collection of data for the primary analysis.

Subject-level End of Study Date

End of study for each subject is defined as the date of the subject last study assessment

in the study. The date subject ended the study is recorded on the End of Study

electronic case report form (CRF).

Study-level End of Study Date

End of study for the study is defined as the date when the last subject is assessed or

receives an intervention for evaluation in the study following any additional parts in the

study (ie, safety follow-up) as applicable.

5.2 **PK/PD Parameters** 

**AUC**last

AUClast is specifically defined in this study as the area under the concentration time

curve measured from the time of drug administration to the beginning of the next

dialysis session, following the first and last dose.

 $C_{max}$ 

 $\underline{C_{\text{max}}}$  is defined as the maximum observed **plasma** drug concentration **measured** 

between the time of drug administration to the beginning of the next dialysis

session.

5.3 **Demographics and Baseline Related Definitions** 

Age

Age will be collected as the subject's age in years at enrollment as recorded on the

eCRF.

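### The TEAE window is cut at the subject's last study assessment, so a new adverse event after an early exit can be left out of the treatment-emergent tables even within days of a dose

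*SAP*

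**What the plan says.** SAP 5.4 defines a treatment-emergent adverse event (TEAE) as one that starts on or after the first dose and "up to 30 days after the last dose date or EOS date, whichever is" earlier. The main adverse event table in SAP 9.6.1 is restricted to TEAEs.

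The EOS date is set in SAP 5.1: "End of study for each subject is defined as the date of the subject last study assessment". The next sentence there adds "The date subject ended the study is recorded on the End of Study" eCRF, without saying which date is entered after a death, a withdrawal or loss to follow-up. The protocol glossary agrees with the SAP definition; for an individual subject, end of study is "defined as the last day that protocol-specified procedures are conducted for an individual subject". For a subject who completes, protocol 7.2.3 says "Subject participation is complete once Day 55 end-of-study (EOS) procedures are performed".

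Collection runs on a different clock. Protocol 9.2.2 requires serious adverse events (SAEs) to be recorded "through 30 days after the last dose of investigational product or Day 55 End of Study, whichever is later". Protocol 9.2.1 collects non-serious events through Day 55.

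**The concern.** The EOS limb shortens the window for exactly the subjects who leave early. An acute event that begins between visits and leads the subject not to return starts after the last assessment. The rule then treats it as not emergent however close it is to a dose. Protocol 2.3 lists hypocalcemia, QT prolongation, worsening heart failure and ventricular arrhythmia among the important risks, so the days just after a dose matter.

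Incidence of adverse events is a secondary endpoint, and the second study hypothesis is that the drug is safe and well tolerated. With about 24 active and 8 placebo subjects, one event counted or not counted is visible in the table. Where the fatal or serious event tables do show such an event, they would disagree with the TEAE table, and the SAP gives no rule for explaining the difference.

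**Working it through.** **The plan's own figure.** The documents give no figure for the TEAE window. The only adverse event figures are the detection probabilities in SAP 3.2, and they reproduce: 1 − 0.99^24 = 21.4% (stated 21%) and 1 − 0.85^24 = 98.0% (stated 98%). They are not in dispute.

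**Inputs.**
- Dosing days (protocol 7.2.3): 1, 3, 6, 8, 10, 13, 15, 17, 20, 22, 24, 27.
- Later visits (Schedule of Assessments): Days 28, 29, 34, 41, 55.
- Early-termination visit (Table 1a, footnote a): about two days after the last dose, on a best-effort basis.
- EOS: date of the last study assessment (SAP 5.1).

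**Formulas.** With d the last dose day and v the last assessment:
- the TEAE window closes at min(d + 30, v);
- SAE collection closes at max(d + 30, 55);
- days within 30 days of the last dose that are lost = (d + 30) − min(d + 30, v).

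| Last assessment v | d | d + 30 | Window closes | Days lost |
|---|---|---|---|---|
| Any dosing visit, v = d | d | d + 30 | d | 30 |
| Early-termination visit, v = d + 2 | d | d + 30 | d + 2 | 28 |
| Day 28 | 27 | 57 | 28 | 29 |
| Day 29 | 27 | 57 | 29 | 28 |
| Day 34 | 27 | 57 | 34 | 23 |
| Day 41 | 27 | 57 | 41 | 16 |
| Day 55 (completer) | 27 | 57 | 55 | 2 |

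The first row holds for each of the 12 dosing days.

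**One subject followed through.** Last dosed and last assessed on Day 10, with a new SAE starting on Day 11:
- As written: min(40, 10) = Day 10, so the event is not a TEAE.
- SAE collection: max(40, 55) = Day 55, so the event falls within the collection period.
- If the event is a death and the eCRF end date is the date of death: min(40, 11) = Day 11, so the event counts.
- If the window is not cut at EOS: it closes on Day 40, so the event counts.

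**Where the last-dose limb decides instead.** If the last dose is on Day 24 or earlier and the subject stays to Day 55, d + 30 comes first (24 + 30 = 54). EOS then has no effect.

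**Completers.** With the last dose on Day 27, SAEs are collected to max(57, 55) = Day 57, but the TEAE window closes at min(57, 55) = Day 55. Serious events starting on Days 56 and 57 are collected and are not TEAEs.

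**Effect of one omitted subject.** 1/24 = 4.2 percentage points in the active arm; 1/8 = 12.5 points in the placebo arm.

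**The case against.** A reader might infer that any death or hospitalization that ends participation is dropped, and that the worst events disappear from the safety report. The documents do not support that.

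- **The eCRF date.** SAP 5.1 also refers to the end date on the eCRF, and protocol 8.2.2 lists death as a reason for removal from study. The date of death is a natural entry, and a fatal event would then count. This stands as an uncertainty: the SAP's defining sentence points to the last assessment, and nothing says which date prevails.
- **Start date governs.** An event that began on or before the last assessment and later became serious or fatal remains a TEAE. This stands.
- **Hospitalization is not an exit.** It is not among the protocol 8.2.2 reasons, so a hospitalized subject stays in the study unless another reason applies. This stands, and it narrows the problem to subjects who actually leave.
- **Separate tables.** SAP 9.6.1 provides fatal, serious and withdrawal tables that are not worded as treatment-emergent. The event need not vanish from them. It would still be missing from the main table.
- **Wider meaning of assessment.** Protocol 7.3.17 speaks of adverse event assessments throughout the study, so the contact at which staff learn of the event could count as a later assessment. This is possible, but the glossary ties EOS to protocol-specified procedures, and the SAP does not adopt the wider reading.
- **Collection and analysis may differ.** Protocol 9.2.2 governs reporting, and an analysis window need not match it. This is fair: the difference between the later and the earlier date is not in itself an error. Protocol 8.1 also limits analysis to data up to withdrawal of consent, apart from the provision that "publically available data can be included after withdrawal of consent" where permitted. That leaves new events between the last assessment and the withdrawal of consent, and events after other kinds of exit.
- **Another parsing.** The clause could mean 30 days after the earlier of last dose and EOS. Because the last dose never follows EOS, that reading makes the EOS term redundant, so it is unlikely to be intended.

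**Conclusion.** The point holds in limited form. As SAP 5.4 and 5.1 are written, a new-onset event after the last assessment of a subject who leaves early is not treatment-emergent, even within days of a dose. Examples are a non-fatal SAE after a withdrawal, or a death if the eCRF end date is the last visit. Between 16 and 30 of the 30 days after the last dose can be lost for an early leaver, depending on the last assessment, and 2 for a completer last dosed on Day 27.

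The conclusion assumes that EOS is the last assessment as defined and that the event was recorded. The number of subjects affected is likely small and cannot be derived from the documents, which give no rate of early departure and no rate of events after departure. The table shows truncated windows, not lost events. The stronger inference, that deaths and serious events are removed from all safety tables, does not follow.

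**What to change.** In SAP 5.4, define TEAEs as recorded adverse events that start on or after the first dose and through 30 days after the last dose, and state that the subject-level EOS date does not cut this window. Apply the same definition to every table described as treatment-emergent or treatment-related, including the hypocalcemia table.

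Whether to count events that start more than 30 days after the last dose but by Day 55 is a separate choice and is not needed here. Replacing the earlier date with the later one would settle that choice too: a subject dosed once who stays to Day 55 would then have events up to 54 days after the dose counted.

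The cost is one sentence in the SAP and one programming line, with no new data collection. The small downside is that a few events after the last visit, with less complete information, would be counted.

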#### Adverse Event Subject Incidence

Defined as the number and percentage of subjects with a reported event(s). For subjects with multiple reports of the same event during the study, the subject will be counted only once. For adverse event tabulations involving severity, the highest severity of the particular adverse events will be used for each subject.

#### Adverse Events of Interest (EOI)

Adverse events of interest are defined by the most current standardized product-level event of interest list. Unless otherwise specified, the narrow search scope will be used for all EOIs.

#### **Concomitant Medications of Interest**

The selected medications of interest are: nutritional vitamin D (vitamin D supplement), vitamin D sterol (active vitamin D), calcium supplements, and phosphate binders, as identified in the concomitant medication CRFs.

